7.3 Statistical analyses

7.3.1 *Analysis of the primary endpoints*

The unit of analysis is at the patient-level. All analyses will use intention-to-treat principles. We will use generalized estimating equations to adjust for clustering and repeated observations per provider to evaluate the effectiveness of the intervention arms versus usual care. For the inappropriate prescribing outcome, we will use a log link function and binary distributed errors. These models generate the estimated relative risks (RRs) with robust standard errors and are considered to be particularly appropriate when outcomes are common (e.g., incidences of $\geq 10\%$). Because this is a randomized trial, our primary analyses are

planned as unadjusted; however, in secondary analyses, we will adjust for patient age, race/ethnicity, and gender.

Given the nature of the data and how the outcomes are categorized, there will not be missing values for the primary endpoint, as the absence of action is classified as no action by the provider. For the primary analysis, we will include all eligible patients in the denominator who had at least one visit with their primary care provider. In secondary analyses, we will include all eligible patients of those primary care providers in the denominator, regardless of whether the patient visited the provider over the follow-up period.

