3.2 Overall design

We will conduct a parallel group trial at Mass General Brigham, specifically within MGH primary care practices. We hypothesize that these tools will reduce prescribing of high-risk medications (primary outcome), cumulative prescribing of high-risk medications (secondary outcome), and clinically-significant adverse drug events like sedation and confusion (tertiary outcome) compared with usual care.

3.2.1 *Trial Design*

[figure not shown]
This trial is a cluster-randomized, NIH-defined Phase III pragmatic trial. The study statistician, in partnership with data analysts at MGB, will generate and implement the randomization scheme, with oversight by the Principal Investigators. All the study sites will be at MGH for this trial; we have received approval from leadership at MGH primary care practices and Digital Health eCare teams to conduct this trial. For study evaluation, data regarding patients' medical history, disease control, medication use, and healthcare utilization will be obtained from EHR data or administrative claims data. Any administrative claims data used for evaluation in this study will come directly from MGB in HIPAA-limited datasets through their risk-bearing contracts.

We will randomize primary care providers at MGH to one of the 2 most promising treatment arms identified in the prior adaptive randomized trial conducted at Atrius Health or usual care (described in further detail in 5.2). We expect to randomize approximately 200 providers. Providers randomized to one of the 2 selected treatment arms will receive an EHR tool to guide their care of eligible patients. We will randomize providers based on provider demographic characteristics, patient case-mix factors, and baseline rates of high-risk medication prescribing measured in EHR data.

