5.3 Measures to minimize bias: randomization and blinding

Providers will be randomized to treatment arms in equal proportions based on blocks. We will use provider-based cluster randomization to minimize the possibility of contamination in study interventions between practices and clinic staff. For the randomization, we will use stratified randomization based on clinic practice size and baseline rates of prescribing to reduce potential imbalances between the providers assigned to the treatment arms.

The providers will not be blinded to which arm they were assigned to, as blinding is the context of an intervention that is intended to motivate action will be infeasible. The study

analyst will generate and implement the randomization scheme, with oversight by the Principal Investigators. Investigators will be blinded to the treatment arms during interim and final analyses.

6. Study Assessments and Procedures

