7.2 Sample size determination

We should have >80% power to detect absolute differences of 10% or smaller in the reduction in prescribing between each intervention arms and usual care, assuming an intra-provider correlation of 0.1 (which is based on prior work including the Atrius trial) and a baseline rate of the primary outcome of 25% in the usual care arm. We plan to use Holm-Bonferroni correction to account for multiple testing between each of the intervention arms and usual care, but we will be powered even if using a Bonferroni correction. Our assumptions will also be robust to a slightly higher baseline rate of the primary outcome in the usual care arm. We should also be sufficiently powered to detect meaningful differences in the clinically significant adverse events.

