In secondary analyses, we will control for potential confounders which will be measured using EHR data from structured fields and administrative claims data. These variables will include provider characteristics (such as specialty, age, and gender), patient characteristics (such as major comorbidities, race/ethnicity, and age), and practice characteristics (such as practice size).

8. Ethical and regulatory requirements

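### Providers are randomised within strata, but the primary GEE leaves the stratification factors out; if those factors predict the outcome, its standard error is too wide and some power is given up

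*Combined protocol and SAP*

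**What the plan says.** Randomisation (5.3): "Providers will be randomized to treatment arms in equal proportions based on blocks", and "we will use stratified randomization based on clinic practice size and baseline rates of prescribing to reduce potential imbalances". Section 3.2.1 gives a different list of factors: "We will randomize providers based on provider demographic characteristics, patient case-mix factors, and baseline rates of high-risk medication prescribing measured in EHR data". It also gives the number of clusters: "We expect to randomize approximately 200 providers", over two active arms and usual care.

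Primary analysis (7.3.1): a GEE clustered on provider, with log link and robust standard errors. The primary analyses are "planned as unadjusted; however, in secondary analyses, we will adjust for patient age, race/ethnicity, and gender". The reason given is that the trial is randomised.

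Other places where the factors might enter a model:
- 7.3.2 allows adjustment for strong predictors left unbalanced by the stratification, but only at patient level and under the secondary endpoints.
- 7.3.5 plans secondary analyses that include "practice characteristics (such as practice size". Baseline prescribing is not named there, but the lists are open.
- 6.1 collects baseline prescribing rates in order to assess imbalance, not as a model term.

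Power (7.2): "We should have >80% power to detect absolute differences of 10% or smaller in the reduction in prescribing", with an intra-provider correlation of 0.1 and 25% in usual care, "but we will be powered even if using a Bonferroni correction". The planned procedure is Holm-Bonferroni.

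**The concern.** Stratified blocks balance the arms on the strata, so differences between strata drop out of the treatment contrast. A robust standard error clustered on provider, from a model without stratum terms, still counts them. Randomisation, the plan's stated reason for not adjusting, supports an unbiased estimate. It does not make the standard error match a stratified design. If the strata are prognostic, the test runs below its nominal alpha and loses power.

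What is at stake is efficiency only. It deserves attention because there are only about 67 providers per arm, so between-provider variance is a large part of the standard error, and the strata are the design's own means of reducing it. Covariates also need to be fixed before outcomes are seen.

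**Working it through.** **Inputs from the documents.** About 200 providers in three equal arms (about 67 per arm); ICC 0.1; 25% against 35%; two comparisons with usual care under Holm.

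**Assumptions.** Overall two-sided alpha 0.05, so 0.025 per comparison at the Bonferroni level; m patients per provider; R, the share of between-provider variance explained by the strata. The documents give none of these.

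**1. The plan's own power figure.** Variance per arm = [p(1-p)·ICC + p(1-p)(1-ICC)/m]/67, and p(1-p) summed over the two arms is 0.1875 + 0.2275 = 0.415. At m = 14:
- SE = √[0.415 × (0.1 + 0.9/14)/67] = 0.0319.
- Power at alpha 0.025 = Φ(0.10/0.0319 - 2.241) = 81.4%.

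At m = 12 and 13 power is 78.7% and 80.2%. The Bonferroni-level claim therefore holds from about 13 or 14 patients per provider. Since m is not stated, the claim is neither confirmed nor refuted. I use m = 14 below.

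**2. How much too wide the standard error is.** At m = 14 the between-provider share of the variance is 0.1/(0.1 + 0.0643) = 61%. The true variance multiplies the ICC term by (1-R), but the unadjusted standard error does not:

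ratio = √[(0.1 + 0.0643)/(0.1(1-R) + 0.0643)]

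Power without the strata is Φ((0.10 - z·SE_reported)/SE_true). Power with them is Φ(0.10/SE_true - z).

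| R | SE too wide by | Power at alpha 0.025, strata out → in |
|---|---|---|
| 0 | 0% | 81.4 → 81.4% |
| 0.10 | 3.2% | 82.2 → 84.0% |
| 0.25 | 8.6% | 83.4 → 87.8% |
| 0.50 | 19.9% | 85.8 → 93.5% |

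These gains ignore the small-sample correction that the adjusted model needs, so they are upper figures.

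**3. Net effect with the correction, under Holm.** This was simulated with 20,000 trials per setting: three arms, 200 providers, m = 14, blocks of 6 (assumed), beta-binomial providers and a Poisson log-link GEE with independence working correlation. The planned model is unadjusted and uncorrected. The alternative has stratum terms and a full leverage correction. With 4 strata:

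| R | Power per comparison, planned → adjusted | Net (points) | Family-wise error, planned / adjusted |
|---|---|---|---|
| 0 | 85.5 → 84.4% | -1.1 | 5.2 / 4.6% |
| 0.10 | 85.5 → 86.0% | +0.5 | 4.4 / 4.6% |
| 0.25 | 87.3 → 90.0% | +2.7 | 3.2 / 4.6% |
| 0.50 | 89.3 → 94.8% | +5.5 | 1.6 / 4.3% |

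With 9 strata the net changes are -1.7, -0.2, +2.1 and +5.4 points. In the 4-stratum simulations the unadjusted standard error exceeds the empirical SD by 2, 8 and 18% at R = 0.10, 0.25 and 0.50, slightly below the analytic figures.

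**4. Many cells entered individually.** Same design, 6,000 trials per setting, at R = 0, 0.10 and 0.25:
- 18 cells: -3.5, -1.5, +2.2 points.
- 27 cells: -5.8, -3.3, +0.6 points. A repeat at 27 cells and R = 0 gave 84.6 → 78.9%.

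Without a correction, the adjusted model's family-wise error is 5.1 to 5.8% with 4 or 9 strata, 6.1 to 7.0% with 18 and 7.4 to 8.0% with 27.

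**5. Separate check of direction.** A two-arm simulation (132 providers, 4 strata, m = 10, R = 0.25, 1,500 runs) gave an empirical SD of the log relative risk of 0.113. The mean unadjusted standard error was 0.124 and the mean adjusted one 0.113.

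**The case against.** The strongest reply is that no error is shown. An unadjusted primary analysis is an explicit and valid choice, and any benefit of changing it rests on R, which no section gives. That stands.

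A gain of practical size also needs a strong association. If one normally distributed factor cut at its median carried all of it, the split would keep 2/π (64%) of the explained variance. R = 0.25 would then need an underlying correlation of √(0.25/0.637) = 0.63, and R = 0.50 would need 0.89. The factor is a prescribing rate, whereas the outcome is discontinuation or taper among patients already prescribed, so a strong link cannot be taken for granted. This stands too, and it is why 25 to 50% is an upper range and not an expectation.

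Larger panels shrink the gain: at R = 0.25 and alpha 0.025 the analytic figure is 4.4 points at m = 14, 3.1 at m = 30 and 2.3 at m = 50. The number of strata is also unknown, and with many cells adjustment can cost more than it returns. Both limits are accepted, and the second shapes the fix.

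The secondary analyses in 7.3.5 do not answer the point, because they do not change the primary test.

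A reader might infer more than the documents support:
- That the trial is underpowered, or that the primary test is biased or anti-conservative because of the omission. Neither follows: the omission makes the test conservative, and only if the strata are prognostic.
- That baseline prescribing is barred from every adjusted model. It is unnamed in 7.3.5, not excluded.
- That adjusting never costs more than a point or two. That holds for about 9 cells or fewer.

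**Conclusion.** The concern holds as one of efficiency, and the change is worth making as a cheap improvement. The plan stratifies and then leaves the factors out of its primary model. At 14 patients per provider the standard error is about 3, 9 or 20% too wide if the factors explain 10, 25 or 50% of between-provider variance, and exact if they explain none.

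With few strata and a small-sample correction, net power under Holm changes by about -1 to -2 points with non-prognostic factors, about zero at 10% explained, and about +2 to +5 points at 25 to 50%. The documents neither support nor refute that upper range. With about 18 to 27 cells entered individually, the loss can reach about 3 to 6 points.

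The sizes rest on assumed values of m, R, alpha, block size and number of strata; the direction does not. The mismatch between 3.2.1 and 5.3 is a separate documentation point and does not make this one more serious. It does have to be settled first, since the strata cannot be identified until it is.

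**What to change.** 1. Reconcile the randomisation factors in 3.2.1 and 5.3, and state the strata, their cut-points and their number.
2. In 7.3.1, prespecify the primary analysis as the provider-clustered log-link GEE with the stratification factors as covariates in parsimonious form: main effects of each factor, or cell indicators only if there are about 9 cells or fewer. As an illustration, three factors at three levels need 6 main-effect terms instead of 26 cell terms. The main-effects form was not simulated separately.
3. Name the small-sample correction to the robust standard error.
4. State that Poisson errors with log link and robust standard error will be used if the log-binomial model does not converge.
5. Keep the unadjusted relative risk as a sensitivity analysis.

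The cost is SAP wording once item 1 is done. No new data are needed: the strata are fixed before randomisation, and baseline prescribing is already collected under 6.1. The price is the 1 to 2 points of power if the factors turn out not to be prognostic. Part of that only removes the uncorrected unadjusted test's own slight excess error (5.2% family-wise against 5%).

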5.2 Study interventions

Physicians in the replication trial randomized to one of the 2 active intervention arms will receive one of several possible enhanced EHR decision support to guide care. The type and timing of an alert will vary based on the intervention are outlined below. The two specific EHR tools for the replication trial at MGB was determined based on the adaptive randomized trial results:

Arm	Alert type	Open encounter	Follow-up booster	Pre-commitment
1	Enhanced	X	X	
2	Enhanced	X		X
Usual care	None			

Arms 1 through 2 are enhanced EHR tools to encourage the deprescribing of the medications under study. Physicians randomized to usual care will receive no intervention.

The central component of Arms 1 through 2 will be an enhanced EHR alert (known as a Best Practice Advisory [BPA]). The enhanced BPA will appear on each provider's EHR screen and will contain several standard components. The BPA will:

1. give providers information about why the medication is dangerous for their patient using the behavioral science principle of salience to make this information as impactful as possible;
2. include a set of tips to help providers discuss medication discontinuation with their patients;
3. ask providers to select an acknowledgment reason if they decided not to discontinue the medication;

4. include a SmartSet order set that will allow providers to order a gradual dose taper for their patient, which limits risks of withdrawal symptoms for the patients for benzodiazepines and sedative hypnotics, order alternative medications, place a referral to a behavioral health specialist, provide instructions on how to make lifestyle modifications to improve patient symptoms, and add customizable patient instructions for how to gradually taper off benzodiazepines and sedative hypnotics, as applicable.

We will also test several other modifications to this enhanced BPA. In specific, as outlined in the table above, we will add in a boosting option in the enhanced BPA in Arm 1, which is a provider-directed option for a follow-up in-basket message sent 4 weeks after the BPA is triggered. Arm 2 will test the use of a two-staged pre-commitment BPA in which the providers are prompted to discuss risks of these high-risk medications and share a handout about the risks with their patients, at their own discretion.

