6.2 Outcomes

The primary outcome will be a binary composite measure of a reduction in inappropriate prescribing, evaluated using EHR data. In specific, we will measure a composite of 1) discontinuation of high-risk medications (benzodiazepines, sedative hypnotics, or anticholinergics) defined by either: a) active discontinuation and no subsequent order or b) no order during follow-up or 2) ordering a gradual dose taper (for benzodiazepine or sedative hypnotics). Our primary analyses will be within patients who had a visit (telemedicine or in-person) with a study provider after randomization. If either of these actions is taken by providers for a specific patient at any point in the follow-up window, we will classify the patient as having had a reduction in inappropriate prescribing. If the patient has multiple therapeutic classes of interest (e.g., benzodiazepines and sedative hypnotics), we will classify patients with a reduction for any class as a “reduction” for the composite measure. We will also stratify

patients by their number of eligible therapeutic classes (i.e., one, two, or three classes) and analyze outcomes within these strata.

Secondary outcomes include the quantity of high-risk medication prescribed, defined by number of pills of high-risk medications (all three classes) prescribed to patients in the follow-up period and number of lorazepam milligram equivalents of benzodiazepines and sedative hypnotics to capture cumulative prescribing by all providers. As above, we will also stratify patients by their number of eligible therapeutic classes (i.e., one, two, or three classes) and analyze outcomes within these strata.

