7.3.2 Analysis of secondary endpoints

For the secondary outcome of cumulative medication prescribing, we will use an identity link function and normally distributed errors within the generalized linear models. For tertiary adverse clinical outcomes and resource utilization outcomes, we will use a log link function and binary distributed errors. These models generate the estimated relative risks (RRs) with robust standard errors and are considered to be particularly appropriate when outcomes are common (e.g., incidences of $\geq 10\%$). For these outcomes from claims data, we will follow patients whose providers are randomized to the study from the time of randomization until they are censored due to loss of continuous enrollment in their health plan. Due to the nature of the randomization, we do not anticipate any systematic differences in the amount of follow-up time per arm but will account for any imbalances using inverse probability censoring weights.

Because this is a randomized trial, our primary analyses are planned as unadjusted; however, if there are strong patient-level predictors of the outcomes not balanced by stratified randomization, we will adjust for these. Given the nature of the data and how the outcomes are being measured, there should not be missing values. However, should there be sufficient missing data (e.g., $> 10\%$), we will use multiple imputation.²⁵

7.3.3 *Baseline descriptive analyses*

We will report the means and frequencies of pre-randomization variables separately for intervention and control subjects. Comparisons of these values will be performed using t-tests and chi square tests and their non-parametric analogs, as appropriate. The outcomes will be evaluated using intention-to-treat principles among all randomized patients.

7.3.4 *Subgroup analyses*

In subgroup analyses, we will explore whether there were any modifiers of the effects of the EHR tools. For example, we will explore if certain types of providers (e.g., by specialty) were more likely to respond to the EHR tools or if there were observable differences in patients who were less likely to receive inappropriate medications, such as gender or race/ethnicity.

7.3.5 *Exploratory analyses*

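### The primary analysis keeps only patients with a visit after randomization yet is labelled intention-to-treat, and no by-arm comparison of who visits is planned

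*Combined protocol and SAP*

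**What the plan says.** Two places restrict the primary analysis to visitors. Section 6.2: "Our primary analyses will be within patients who had a visit (telemedicine or in-person) with a study provider after randomization". Section 7.3.1: "we will include all eligible patients in the denominator who had at least one visit with their primary care provider". They differ in whose visit counts: any study provider in the first, the patient's own primary care provider in the second.

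Two places describe a wider population. Section 7.3.1 opens with "All analyses will use intention-to-treat principles". Section 7.3.3 ends with "The outcomes will be evaluated using intention-to-treat principles among all randomized patients". Since providers are the randomized units, that last phrase is most naturally read as all eligible patients of randomized providers.

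Section 7.3.1 also plans a secondary analysis of all eligible patients "regardless of whether the patient visited the provider over the follow-up period".

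On exposure, Section 5.3 states "The providers will not be blinded to which arm they were assigned to". The table in Section 5.2 places the alert at "Open encounter" in both active arms. Arm 1 adds "a provider-directed option for a follow-up in-basket message sent 4 weeks after the BPA is triggered".

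Sections 6.1 and 7.3.3 plan baseline comparisons between arms, but do not tie them to visit status. No section compares the share of patients who visit.

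**The concern.** Randomization balances all eligible patients of the randomized providers. It does not guarantee balance in the subset who later visit, unless visiting is unaffected by arm. The plan therefore claims for its primary analysis a property that this analysis lacks.

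Whether this matters numerically depends on two things: whether the arms differ in who visits, and whether visiting is related to the outcome. The second is plausible. Under Section 6.2 a patient counts as a success when no further order is placed in follow-up, which can happen with no contact at all, so visitors and non-visitors may have different outcome rates. The first is possible but undocumented. Providers know their arm, and once a provider has seen a first alert, later patients make their first visits to a provider who has already been prompted. If visiting did differ, the primary relative risk would compare differently selected patients, and no planned table would show it.

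**Working it through.** **The plan's own figure.** Section 7.2 claims more than 80% power for 25% versus 35% with an intra-provider correlation of 0.1. Patients per provider are not given, so the figure can only be bracketed. With about 67 providers per arm (200 over three equal arms) and a two-sided level of 0.025 per comparison (assumed: 0.05 halved; the plan states no alpha), power is about 75%, 82% and 86% with 10, 15 and 20 analysed patients per provider. About 14 are needed for 80%. The claim is attainable, and this point does not dispute it.

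**Size of a selection effect.** The plan gives no visit share, so there is nothing to reproduce here. Inputs:

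- outcome rate among usual-care visitors: 25% (Section 7.2, which does not say whether this refers to visitors or to all eligible patients)
- v, the usual-care visit share: 85% (assumed)
- d, the extra share visiting in the intervention arm: 2 or 5 points (assumed)
- r, the outcome rate in those extra visitors: 10%, 25% or 50% (assumed)
- no true effect of the tool

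Visitor rate in the intervention arm = (v × 0.25 + d × r) / (v + d), so the shift is d × (r − 0.25) / (v + d).

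| d | r | Intervention visitors | Shift, points | RR |
|---|---|---|---|---|
| 0.02 | 0.10 | 0.2145/0.87 = 24.7% | -0.3 | 0.99 |
| 0.05 | 0.10 | 0.2175/0.90 = 24.2% | -0.8 | 0.97 |
| either | 0.25 | 25.0% | 0 | 1.00 |
| 0.02 | 0.50 | 0.2225/0.87 = 25.6% | +0.6 | 1.02 |
| 0.05 | 0.50 | 0.2375/0.90 = 26.4% | +1.4 | 1.06 |

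The shift is zero when r equals 25%, or when d is zero and the visitors are of the same kind in both arms. Equal shares alone do not guarantee the latter.

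**Effect on the error rate.** Assume 15 analysed patients per provider. The effective size per arm is 67 × 15 / (1 + 14 × 0.1) = 1005/2.4 = 418.75. The standard error of the difference is √(2 × 0.25 × 0.75 / 418.75) = 0.0299. With δ = shift/SE, two-sided rejection at 0.025 is Φ(−2.241 + δ) + Φ(−2.241 − δ). For +0.6 points (δ = 0.19) this is 2.8%, and for +1.4 points (δ = 0.46) it is 4.1%, against a nominal 2.5%.

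**Stress case.** With 80% versus 90% visiting and r from 10% to 60%, the shift runs from (0.20 + 0.01)/0.90 − 0.25 = -1.7 points to (0.20 + 0.06)/0.90 − 0.25 = +3.9 points. At the upper end, rejection at nominal 2.5% is about 14% to 18% with 10 to 20 patients per provider. Nothing in the documents suggests a gap this large.

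**The case against.** The strongest defence is that an encounter-triggered tool can act only on patients who are seen. Restricting to them, by a rule that is identical in all arms and does not depend on receiving an alert, is a sensible way to avoid dilution. That stands. So does the cost of the alternative. If 80% visit and non-visitors have a 25% outcome rate in both arms, a 10-point effect in visitors becomes 0.8 × 35% + 0.2 × 25% = 33% versus 25%, or 8 points. Over assumed visit shares of 70% to 90%, non-visitor rates of 25% to 60% and 10 to 20 visitors per provider, all-eligible power at 0.025 is 43% to 79%, against 75% to 86% in visitors only.

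It is also fair to say that the all-eligible analysis is already planned, and that for any one patient the alert normally fires at or after the visit that brings that patient into the set.

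A reader might infer that alerted providers call patients in and so inflate the apparent benefit. The documents do not support that. Section 5.2 describes no recall or outreach, and the Arm 1 message follows that same patient's own alert. Nor do they say whether an encounter that is not a visit can trigger the alert, so no loss of outcomes by that route can be claimed.

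What the defence leaves untouched is the label, the conflict between sections, and the absence of any by-arm description of visitors.

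**Conclusion.** The point holds as one of labelling and an unexamined selection step. The primary set is conditioned on a post-randomization visit, it is called intention-to-treat, Section 7.3.3 names a different population, and no planned output would show whether visiting differs by arm.

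Bias is possible but not demonstrated, and its direction is unknown. Under the main assumptions above it is -0.8 to +1.4 points, small beside the 10-point design difference. Visit shares, extra visitors' outcome rates and patients per provider are all assumed.

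A reader might also conclude that the all-eligible analysis should take over whenever visit proportions differ. That does not follow. With 15 patients per provider, 67 providers per arm, an assumed visit correlation of 0.02 to 0.1 and a two-sided 0.05 test, 85% versus 87% would be detected only 13% to 21% of the time: the standard error is √((0.85 × 0.15 + 0.87 × 0.13)/n), with n = 1005/1.28 = 785 or 1005/2.4 = 419. Such a trigger would be unreliable, and acting on it would move the conclusion to a diluted estimate after the data are seen.

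**What to change.** In Sections 7.3.1 and 7.3.3, with Section 6.2 brought into line:

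1. Describe the primary set as eligible patients with a qualifying visit after randomization. Use one definition of whose visit counts, and reserve the term intention-to-treat for the all-eligible analysis. Reconcile the three sections accordingly.
2. Report by arm the proportion of eligible patients with a qualifying visit, using the same provider-clustered GEE, together with the visitors' baseline characteristics.
3. Report the all-eligible result beside the primary result for both intervention-versus-usual-care comparisons, and interpret the primary result in light of any difference in visiting. Do not add a rule that switches the primary analysis.

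The cost is SAP wording and one extra table; both analyses are already planned. The price is that the primary result can no longer be described as intention-to-treat.
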